2.1 Name and description of the study

Name: Daily Delivery and Supervision of Psychotropic Medication for High-Risk Patients with Severe and Persistent Mental Illness

The present study seeks to evaluate the effectiveness of an innovative and collaborative voluntary program for facilitating adherence to medication. This program involves partnering with the patient to develop a treatment plan and then collaborating with a pharmacy who hire staff specifically for the purpose of delivering and observing the patients taking their medication. The program is designed to serve individuals with severe and persistent mental illnesses who have been repeatedly hospitalized, are repeat users of community crisis services, or are frequently in contact with the criminal justice system.

The current study will follow high-risk and high need patients who have severe and persistent mental illness and who are involved with Forensic Services. Forensic Services is a multidisciplinary program based out of the PsycHealth building (Health Sciences Centre campus) and is part of the teaching program at the University of Manitoba's Department of Psychiatry, College of Medicine. The program provides assessment reports for the courts and psychiatric care to accused persons who have been found Not Criminally Responsible for criminal offences because of a mental disorder, or have been found Unfit to stand trial. It also provides care to offenders who have a mental illness and need supervision to manage their risk in the community. The pharmacy partner offering daily dispensing services is Leila Pharmacy [name] (Contact: [name], pharmacist) who delivers these services as part of the pharmacy's professional practice model.

The objective of this evaluation is to determine the impact of the daily dispensing with supervision program on patient well-being and system costs. Expected program benefits include increasing patients' impression of choice and control in their recovery, reduced visits to ER, crisis clinic and hospital admissions, as well as elimination of contacts with the criminal justice system.

2.2 Summary of the known and potential risks and benefits, if any, to the study's human subjects for participating in the study

The expected program benefits include improved patient satisfaction and autonomy, reduced visits to ER, crisis clinic and hospital admissions, as well as elimination of contacts with the criminal justice system.

No potential risks to project participants were identified.

2.3 Description of and justification for the route of administration, dosage, dosage regimen, and treatment period(s) of the modalities given to the study subjects.

'Daily Delivery and Supervision of Psychotropic Medication for High-Risk Patients with Severe and Persistent Mental Illness' is a MPAN-funded project to evaluate the effectiveness of an innovative and collaborative voluntary program for facilitating adherence to psychotropic medication after involvement with the justice system. The program involves a partnership between patients with severe and persistent mental illness and pharmacies who deliver daily dispensing services as part of their operations in hopes of improving patient outcomes such as patient wellbeing, hospitalizations and incarcerations, and in reducing costs associated with therapeutic non-adherence. Patients are supervised by pharmacy staff in their own home as they orally self-administer their regular daily medications to ensure medication compliance.

2.4 Description of the population to be studied.

Individuals with severe and persistent mental illnesses who have been repeatedly hospitalized, are repeat users of community crisis services, or are frequently in contact with the criminal justice system.

2.5 References to literature and data that are relevant to the study, and that provide background for the trial.

Angermeyer, M. C., & Matschinger, H. (2004). The stereotype of schizophrenia and its impact on discrimination against people with schizophrenia: results from a representative survey in Germany. *Schizophrenia Bulletin*, 30(4), 1049.

Canadian Institutes of Health Research. (2012). *Guide to Knowledge Translation Planning at CIHR: Integrated and End-of-grant Approaches*. Canadian Institutes of Health Research.

The program is designed to serve individuals with severe and persistent mental illnesses who have been repeatedly hospitalized, are repeat users of community crisis services, or are frequently in contact with the criminal justice system. There are several objectives of this new approach. First, we believe that these patients are invested in working with our program to stay well, but individual factors related to their personal background or symptoms of their illness contribute to frequent non-adherence to medications. Non-adherence to medications then leads to behaviour that results in frequent use of very expensive services such as the criminal justice system, acute care hospital beds, and crisis services. Working collaboratively with the patient to improve adherence to medications in partnership with a private pharmacy that absorbs costs of the program is a less coercive model than injectable medications, which is the current standard for working with this population. In addition, oral medications are much less expensive than the newer injectable antipsychotics and the costs of running a “depot clinic” where the injectable medications are provided. At this time, there has been no effective program to ensure compliance with oral medications in the published literature.

The purpose of this research is to evaluate the effectiveness of this intervention on recovery by evaluating patient response to the program through a self-reported measure. In addition, we will be evaluating the effect of this low cost program on decreasing the burden of mental health inpatient and crisis services, as well as the burden on the correctional system.

The primary purpose of this study is to evaluate the effectiveness of this new model for decreasing the harmful effects of relapses to psychosis resulting from non-adherence to medications. Specifically, we plan to examine whether or not this program results in less use of crisis services, acute care hospitalization and less contact with the criminal justice system. We plan to assess client satisfaction by conducting Client Satisfaction Measure survey with participants in the new program. We will also engage key stakeholders during the process (e.g., community mental health workers, probation officers, pharmacists) to gather information and suggestions regarding the daily dispensing program. Based on feedback from clients and stakeholders, we will then aim to implement improvements to the process to optimize its effectiveness.

4 Study Design

The scientific integrity of the study and the credibility of the data from the study depend substantially on the study's design. A description of the study design should include:

4.1 A specific statement of the primary endpoints and the secondary endpoints, if any, to be measured during the study.

The primary endpoints to be measured during the study concern how the daily dispensing program will affect medication compliance and outcomes, hospitalizations, re-incarcerations, and community crisis utilization as

well as participants' perceptions of coercion with regards to taking part in the program and satisfaction with the program.

4.2 A description of the type/design of study to be conducted (e.g., before/after design) and a schematic diagram of study design, procedures and stages of analysis. The *before-and-after design is a reasonable option for this evaluation.*

This study proposes to employ a crossover design where data is collected for 12 months during the study and compared to baseline data retrieved for 12 months for each patient before enrollment into the project. Each patient acts as their own control. All individuals currently in the Forensics program will be asked for their informed consent to participate in the study. The study proposes to collect some personal health identifiers such as participant's personal health identification number (PHIN) and date of birth to be able to link medical records for crisis services, hospitalizations and pharmacy data. Patient names will also be collected to determine the number of contacts with criminal services. All personal identifiers will be stripped from the data for analysis and only aggregate data will be reported and/or published.

4.3 A description of the study's intervention.

The main study intervention is the daily supervision of participants while they self-administer their medications by trained pharmacy staff to ensure compliance. The staff in question will be provided by Leila pharmacy and will in addition provide support so that individuals can transition back into living independently through reminders to attend regularly scheduled medical appointments and counseling on correct use of prescribed medications.

Leila pharmacy's LEAP program consists of 3 A'S: adherence, accessibility, and autonomy. Regarding adherence, it is common for individuals taking medications to miss doses. The LEAP program dedicates a team to help individuals living in the community to receive their medications daily at their homes. Staff will also spend some time with each individual to ensure the medications are taken appropriately. Missed or refused doses are recorded and reported back to the Leila pharmacy program coordinator.

With respect to accessibility, access to primary care is a growing problem and there are very few solutions available. This is why the Leila pharmacy team includes a nurse practitioner, dietitian, pharmacist and other allied professionals. The nurse practitioner is available to provide bridging care until a permanent family physician is available. Further, a common cause of medication discontinuation is due to the side-effects. For anti-psychotic medications, weight gain, dyslipidemia and increase risk of developing diabetes can all deter an individual from taking their medications regularly and ultimately derail them from their path to recovery. The Leila pharmacy dietitian is available to any of their clients and they can help address nutritional concerns and develop healthy meal plans. Both these services, like many others, are offered at no additional charge.

Regarding autonomy, staff respect each individual's decision and try to offer support whenever they need assistance. This is why the LEAP program is completely voluntary and their goal is be a transitional program. When an individual has made significant progress, the medical responsibilities are shifted back to the client.

5 Selection and Withdrawal of Subjects

5.1 Subject inclusion criteria.

Individuals currently enrolled in the daily dispensing program that are also part of the Forensics program and suffer from severe and persistent mental illnesses, have been repeatedly hospitalized, are repeat users of community crisis services, and/or are in frequent contact with the criminal justice system.

5.2 Subject exclusion criteria.

Individuals who are not currently in the Forensics program – those who are part of the daily dispensing program, but are not Forensic outpatients.

6 Treatment of Subjects

6.1 Procedures for monitoring subject compliance.

Participants will be visited in home on a daily basis.

7 Statistics

7.1 A description of the statistical methods to be employed, including timing of any planned analysis(ses). Collected data would be analyzed for significant outcomes comparing before and after (a two year total time frame from pre-index date to post-index date) findings for:

- number of days/visits spent with crisis services (ED & CRC),
- hospital visits/admissions (length of stay) and
- number of incarcerations (as a dependent variable)

These data would be entered into a multivariate analysis of covariance (MANCOVA) model or similar multi-level model with baseline or study time, age and gender as the independent variables. Descriptive statistics would be used to elaborate on patient satisfaction and other variables of interest. Preliminary cost analysis will also be undertaken in anticipation of calculating a net benefit for the daily dispensing services.

7.2 The number of subjects planned to be studied.

N = 32

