7.3 The level of significance to be used for any differences

p < 0.05

7.4 Criteria for the termination of the study.

Timeframe of study = approximately one year.

7.5 Procedure for accounting for missing, unused, and spurious data.

Cleaning data, missing data analyses and manual review of data collected etc.

7.6 Procedures for reporting any deviation(s) from the original statistical plan (any deviation(s) from the original statistical plan should be described and justified in protocol and/or in the final report, as appropriate).

All deviations from the statistical plan will be based on the quality of data collected during the study and will be filed as amendments to the protocol with the Ethics Board.

7.7 The selection of subjects to be included in the analyses (e.g., evaluable subjects).

Participants who are currently part of the Forensics program and who are enrolled in the daily dispensing program and have participated in the program for at least one month will be included in the analyses.

8 Ethics

Description of ethical considerations relating to the study.

Ethical considerations relating to the study are that participants may be part of a vulnerable population, and participant characteristics need to be considered as well, such as First Nations individuals. Moreover, the participants are also patients of the principal investigator. To address this issue, the principal investigator will not discuss the study with participants, and will neither encourage nor discourage participation. All study contact will be with a research assistant who is not involved in patient care.

9 Data Handling and Record Keeping

All the data will be maintained in a Redcap database with only authorized individuals having access. All data used for analysis will be stripped of personal identifiers and only aggregate data will be reported.

10 Publication Policy

Publication policy, if not addressed in a separate agreement

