### **Analyses**

A description of the statistical methods to be employed, including timing of any planned analysis(es). Collected data would be analyzed for significant outcomes comparing before and after (a two year total time frame from pre-index date to post-index date) findings for:

- number of days/visits spent with crisis services (ED & CRC),
- hospital visits/admissions (length of stay) and
- number of incarcerations (as a dependent variable)

These data would be entered into a multivariate analysis of covariance (MANCOVA) model or similar multi-level model with baseline or study time, age and gender as the independent variables. Descriptive statistics would be used to elaborate on patient satisfaction and other variables of interest. Preliminary cost analysis will also be undertaken in anticipation of calculating a net benefit for the daily dispensing services.

The number of subjects planned to be studied. N = 32

The level of significance to be used for any differences p < 0.05

Criteria for the termination of the study. Timeframe of study = approximately one year.

Procedure for accounting for missing, unused, and spurious data. Cleaning data, missing data analyses and manual review of data collected etc.

Procedures for reporting any deviation(s) from the original statistical plan (any deviation(s) from the original statistical plan should be described and justified in protocol and/or in the final report, as appropriate).

All deviations from the statistical plan will be based on the quality of data collected during the study and will be filed as amendments to the protocol with the Ethics Board.

The selection of subjects to be included in the analyses (e.g., evaluable subjects). Participants who are currently part of the Forensics program and who are enrolled in the daily dispensing program and have participated in the program for at least one month will be included in the analyses

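### The before-year can include time before entry into Forensic Services, and the model cannot separate that entry from the start of daily dispensing

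*Protocol*

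**What the plan says.** **Eligibility.** Protocol 5.1 takes "Individuals currently enrolled in the daily dispensing program that are also part of the Forensics program". Section 5.2 removes only "Individuals who are not currently in the Forensics program". Both concern status at recruitment; neither sets a Forensics start date or a minimum time in Forensics.

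**Analysis set.** The only duration rule is in 7.7, repeated in the SAP: participants who "have participated in the program for at least one month will be included in the analyses". This reads as time in daily dispensing, and so concerns time after dispensing starts.

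**Comparison.** Under 4.2, study data are "compared to baseline data retrieved for 12 months for each patient before enrollment into the project", and "Each patient acts as their own control". There is no concurrent group. Section 7.1 and the SAP describe "a two year total time frame from pre-index date to post-index date" without defining the index date.

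**Model.** Section 7.1 and the SAP specify a MANCOVA or similar multi-level model "with baseline or study time, age and gender as the independent variables". The outcomes are crisis-service use, hospital use and incarcerations.

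**Forensic Services.** Section 2.1 describes a multidisciplinary program giving psychiatric care. Of its role with offenders it says: "It also provides care to offenders who have a mental illness and need supervision to manage their risk in the community".

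**The concern.** Forensic Services is plausibly an active intervention on the same outcomes as daily dispensing. Take a participant who entered Forensics 4 months before the index date. Eight of the 12 before-months have no forensic care, while the after-year has both forensic care and dispensing. For a participant who has been in Forensics for years, forensic care is present in both periods.

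The plan pools these two kinds of participant. Using patients as their own controls removes stable patient characteristics. It does not remove a second intervention that begins inside the before-window, and no covariate, stratum or sensitivity analysis deals with it.

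The stated objective (2.1) is the impact of daily dispensing with supervision on well-being and system costs. If the pooled change partly reflects Forensics entry, the conclusion about dispensing is affected, and so is the preliminary cost analysis that 7.1 plans as a step towards a net benefit.

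**Working it through.** **Stated figure.** The only planning figure is N = 32 (7.2). It cannot be reproduced, because no power, effect size, standard deviation or event rate is given.

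**Inputs.** From the documents: a 12-month before-window and a 12-month after-window (4.2), N = 32 (7.2), and significance at 0.05 (7.3; two-sided assumed). Assumed, because the documents are silent:

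- f: the share of participants who entered Forensics during the before-year, taken as 25%, 50% and 75%.
- Entry spread uniformly over that year, so a recent entrant has on average 6 of 12 months before entry.
- R: the event rate before forensic care divided by the rate under it, taken as 0.5, 1, 2 and 3.
- No effect of dispensing, and the index date equal to the start of dispensing.

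**Apparent change.** The share of before-period person-time that precedes forensic care is f × 6/12 = f/2. Relative to the rate under forensic care, the average before-rate is 1 − f/2 + R × f/2, and the after-rate is 1. So

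after/before ratio = 1 / (1 − f/2 + R × f/2).

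Example, f = 50% and R = 2: 1 / (1 − 0.25 + 0.50) = 1/1.25 = 0.80, a fall of 20%.

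| f | R = 0.5 | R = 1 | R = 2 | R = 3 |
|---|---|---|---|---|
| 25% | 1/0.9375: rise 7% | 0 | 1/1.125: fall 11% | 1/1.25: fall 20% |
| 50% | 1/0.875: rise 14% | 0 | 1/1.25: fall 20% | 1/1.5: fall 33% |
| 75% | 1/0.8125: rise 23% | 0 | 1/1.375: fall 27% | 1/1.75: fall 43% |

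**Effect on the test.** A simulation ran 20,000 trials of 32 patients per setting, with gamma-Poisson counts (gamma shape 1), no dispensing effect, and a two-sided paired t-test at 0.05 standing in for the planned model. Recent entrants each had exactly 6 months before entry. Rejection rates at 1, 2 and 4 events per year were:

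- no time before Forensics: 0.05 at all three rates;
- 25% recent entrants, R = 2: 0.07, 0.08, 0.12;
- 50% recent entrants, R = 2: 0.13, 0.21, 0.34;
- 50% recent entrants, R = 3: 0.31, 0.51, 0.74.

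With R above 1, nearly all the excess lies on the side of apparent benefit. R below 1 was not simulated.

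**Restricting the before-window.** With before-time limited to time under Forensics and counts turned into rates, the simulated error at 2 events per year was 0.045 (50% recent entrants, R = 2), 0.049 (100%, R = 2) and 0.047 (50%, R = 3). This assumes that the months after entry are representative of time under forensic care.

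**Precision cost of a full-12-month subset.** The detectable standardized paired difference at 80% power (normal approximation) is dz = (1.960 + 0.842)/√n:

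- n = 32: 2.802/5.657 = 0.50;
- n = 16 (f = 50%): 2.802/4 = 0.70;
- n = 8 (f = 75%): 2.802/2.828 = 0.99.

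**The case against.** The strongest reply is that nothing shows the bias exists. It needs participants who entered Forensics within 12 months before the index date, and forensic care that changes the outcomes. The documents quantify neither. If every participant had 12 or more months in Forensics, the problem disappears. This stands, and it limits the point to what can happen.

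A reader might infer that the plan must flatter dispensing. The documents do not support a direction. Time in custody before entry (an assumption) could hold down crisis visits and new incarcerations, and supervision could raise detected contacts. Either would push R below 1 and produce an apparent rise.

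The point also depends on the index date. Section 4.2 counts back from enrollment into the project, while 5.1 recruits people already in dispensing. If the index date is study enrollment, the before-year may itself contain dispensing time, which pulls the contrast towards no difference. The net direction is then uncertain. Fixing the index date at dispensing start would still leave Forensics entry unaddressed.

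Two further inferences go too far. The pooled contrast is not the effect of Forensics plus dispensing, because long-standing Forensics patients had forensic care in both periods; it is a mixture. Nor do those long-standing patients give a clean dispensing contrast, since calendar time, illness course and selection at a point of crisis can still differ between the periods.

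Finally, making a restricted contrast the sole basis for the claim would be costly at N = 32, as the dz figures show. That objection stands, and it is why the restricted analyses belong beside the pooled one.

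**Conclusion.** The gap holds in a conditional form. The eligibility and analysis-set rules require only current Forensics membership, so the before-year can contain time without forensic care. The planned model cannot separate entry into Forensics from the start of dispensing, so a change due to the former can be credited to the latter.

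The size could run from nothing to something that matters: across the assumed f and R, from a fall of 43% to a rise of 23% with no dispensing effect. These figures illustrate sensitivity and do not estimate this study's bias. They rest on uniform entry, the same rate under forensic care for recent and long-standing patients, and an index date at dispensing start. The documents do not support saying that the effect of Forensic Services is in fact credited to dispensing. They support saying that, as planned, a reader could not tell.

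**What to change.** First define the index date and reconcile 4.2, 5.1 and 7.1 on it. Then record each participant's date of entry into Forensic Services and add to 7.1 and the SAP:

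1. A description of the number of participants who entered Forensics during the before-period, and of the before-period person-time and events that precede entry, by outcome.
2. Beside the pooled contrast, two pre-specified sensitivity analyses. One uses person-time rates with before-time limited to time under Forensics care, or enters Forensics status as a time-varying covariate. The other uses only participants with the full 12 prior months in Forensics.
3. A rule that the pooled change is not attributed to dispensing alone if these analyses disagree with it. Disagreement should be defined in advance on estimates and intervals, because in a small subset a p-value above 0.05 says little.

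The pooled contrast should not be labelled as Forensics plus daily dispensing.

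The cost is one extra data field, presumably available from the clinic's records although the documents do not say so, plus SAP wording. The restricted analyses are less precise: at f = 50%, 16 participants remain and the detectable dz is about 0.70 against 0.50. Recent entrants will also have short before-windows, starting just after whatever brought them into Forensics, which may be unrepresentative and should be reported as a limitation. If no participant proves to be a recent entrant, item 1 shows this and the question closes.

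### The hospital outcome is broader than the acute-care aim and does not exclude court-ordered forensic stays, so any such days in the before year could be read as a program benefit

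*Protocol*

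**What the plan says.** The aim and the analysed variable differ in scope.

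- **Aim (protocol section 3):** the program is to be tested for "less use of crisis services, acute care hospitalization and less contact with the criminal justice system". The same section names acute hospital beds among the costly consequences of non-adherence.
- **Endpoint (protocol 4.1):** the list is "medication compliance and outcomes, hospitalizations, re-incarcerations, and community crisis utilization", with hospitalizations unqualified.
- **Analysis (protocol 7.1, and the SAP under Analyses):** the variable is "hospital visits/admissions (length of stay". Neither document adds a facility, ward type, legal status or reason for admission.
- **Population (protocol 2.1):** Forensic Services treats "accused persons who have been found Not Criminally Responsible for criminal offences because of a mental disorder, or have been found Unfit to stand trial". Not every patient of the service falls under such a finding, since the section adds: "It also provides care to offenders who have a mental illness and need supervision to manage their risk in the community".
- **Status and setting (protocol 5.2 and 4.3):** the exclusion covers "those who are part of the daily dispensing program, but are not Forensic outpatients", and the pharmacy team exists to "help individuals living in the community to receive their medications daily at their homes".
- **Comparison (protocol 4.2 and 7.1):** each patient is their own control, with the year before enrollment set against the study year. Hospital data come from record linkage with no stated filter. The model terms are period, age and gender. A preliminary cost analysis is to lead to a net benefit.

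**The concern.** A stay ordered by a court, whether for assessment or under an Unfit or Not Criminally Responsible disposition, depends at least partly on a legal decision. Such a stay can be long, and it is a hospital stay, so nothing in the wording of 7.1 keeps it out.

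The two years are not symmetric for these stays. A person must be an outpatient living in the community to receive supervised doses at home, so someone with a court-ordered stay would usually have finished it before starting the program. The before year carries no such condition. With no comparison group and no term for legal status, the model would attribute the disappearance of those days to daily dispensing. What is at stake is the meaning of a fall in inpatient days, and of any net benefit costed from it.

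**Working it through.** The documents give N = 32 and p < 0.05 but no admission rates, lengths of stay or legal-status counts. There is no figure of the plan's own to reproduce, and everything below except N is an assumption shown over a range.

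**1. Days added to the before year.** If k of 32 patients each had one court-ordered stay of d days in the before year only, the mean rises by x = k × d / 32:

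- 2 × 30 / 32 = 1.9 days
- 4 × 60 / 32 = 7.5 days
- 8 × 180 / 32 = 45 days

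**2. Apparent fall with no program effect.** If acute use is A days per patient in both years, the apparent fall is x / (A + x). A is not in the documents, so three values are used:

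| x (days) | A = 20 | A = 34 | A = 100 |
|---|---|---|---|
| 1.9 | 8.6% | 5.2% | 1.8% |
| 7.5 | 27.3% | 18.1% | 7.0% |
| 45 | 69.2% | 57.0% | 31.0% |

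**3. Admission counts.** Each stay adds at most one admission: 2/32 = 0.06, 4/32 = 0.13 and 8/32 = 0.25 per patient. With one assumed acute admission a year, the apparent falls are 0.0625/1.0625 = 5.9%, 0.125/1.125 = 11.1% and 0.25/1.25 = 20.0%. One admission of 20 days corresponds to the A = 20 column, so the effect on counts is smaller than on days, and much smaller when stays are long.

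**4. Opposite direction for other outcomes.** Inpatient time removes time at risk in the community. Mean before-year exposure falls to 365 − x days. At a constant rate of crisis visits per day at risk, with 365 days at risk in the study year, the count would appear to rise by a factor of 365/(365 − x): 0.5%, 2.1% and 14.1% for the three cases. New incarcerations would behave in the same way.

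**5. False-positive rate for days.** 32 before/after pairs were simulated with no program effect (2,000 runs per case; acute admissions Poisson with mean 1 a year, exponential stays with mean 20 days). A share f of patients had a court-ordered stay of L days in the before year only. Paired tests stood in for the plan's MANCOVA or multi-level model.

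| f | L (days) | Mean apparent fall (days) | False benefit, paired t | False benefit, Wilcoxon |
|---|---|---|---|---|
| 0% | – | about 0 | 2% | 2% |
| 10% | 60 | 5.8 | 11% | 10% |
| 10% | 180 | 17.0 | 26% | 15% |
| 25% | 60 | 14.2 | 40% | 39% |
| 25% | 180 | 42.6 | 85% | 62% |

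The nominal rate in the direction of benefit is 2.5%. The mean falls agree with f × L × (1 − 20/365): for example, 0.25 × 180 × 0.945 = 42.5.

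**The case against.** Four points on the other side have weight.

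- **Scope.** Section 3 can be read as governing, so that hospital use in 7.1 already means acute care. That reading is possible, but neither 7.1 nor the SAP says so, and the analyst would have to choose.
- **Population.** Section 2.1 describes what the service does, not who the 32 participants are. Some may be offenders supervised in the community who never had a court-ordered admission. This stands: the number affected is unknown and could be zero.
- **Window.** Section 5.1 recruits people already in daily dispensing, while 4.2 counts back from enrollment into the project. If dispensing began well before enrollment, a court-ordered stay could predate the before year. This also stands, and it makes the size more uncertain.
- **Cause.** Section 3 argues that non-adherence leads to behaviour that brings patients into the justice system. On that argument some court-ordered stays are relapse harm. Dropping all of them could hide program failures in the study year, particularly as the documents do not say that the incarceration count would capture detention in hospital. This is the strongest point. It rules out simple exclusion as the remedy, but it supports showing the two kinds of stay separately.

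**Conclusion.** The point holds as a gap between aim and outcome. The aim is limited to acute care, the analysed variable is not, and the model cannot separate legal-disposition days from a program effect.

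A reader might infer more: that the plan counts every court-ordered stay, and that the resulting bias favours the program throughout. The documents do not support either. They are silent on whether such stays count and never state that any participant had one. The favourable bias concerns inpatient days and the cost result, and to a lesser degree admission counts; for crisis visits and incarcerations it may run against the program.

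The size is conditional. It could be nil. Over the assumed range it runs from about 2% to 69% of before-year days, depending on how many patients had such stays, how long they lasted and the level of acute use. With 32 patients, a few long stays would be enough to matter. The remedy is cheap and is best settled before the data are examined, because a later choice could be influenced by the result.

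**What to change.** In protocol 7.1 and the SAP:

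1. Classify each hospital stay in both years as acute or court-ordered (assessment, Unfit or Not Criminally Responsible disposition), using the hospital record or the Forensics file. State in advance a rule for stays that change status.
2. Analyse acute admissions and days as the measure of the section 3 aim.
3. Report court-ordered admissions and days separately for both years, and give the all-stays result beside the acute result. Study-year court-ordered stays that follow a relapse or new offence then remain visible.
4. Show the net benefit with and without court-ordered days.
5. Give days at risk in the community for each year, and preferably use them as the denominator or offset for crisis visits and incarcerations.

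The cost is one classification field per stay for about 32 patients, plus SAP wording. The linkage described in 4.2 mentions no legal-status field, so the team should confirm that one of the two sources holds it. Some stays will be ambiguous, and the before-year total may make the program look less favourable.
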